10.3 Visit Windows for Safety Analyses

The table below presents the visits assigned for safety analyses corresponding to the range of treatment study days (window) during which an actual visit (scheduled or unscheduled) may occur. Note that the windows defined for statistical analysis are different from the ones defined in Protocol Section 9.

Visit windows for laboratory tests, vital signs, and for Columbia Suicide Symptoms and Signs Rating Scale (CSSRS):

Derived Visit	Target Study Day [1]	Window [2]
Baseline (for laboratory tests and vitals)	Day 1	Days <= 1
Baseline (for C-SSRS)	Screening (Visit 1)	NA
Visit 2 (for C-SSRS)	Day 1	Days = 1
Visit 3	Day 15	>= Day 2 to <= Day 22
Visit 4	Day 29	>= Day 23 to <= Day 36

Visit 5	Day 43	>= Day 37 to <= Day 50
Visit 6	Day 57	>= Day 51 to <= Day 64
Visit 7	Day 71	>= Day 65 to <= Day 78
Visit 8	Day 85	>= Day 79 to <= Day 92
Visit 9	Day 99	>= Day 93 to <= Day 106
Visit 10	Day 113	>= Day 107 to <= Day 128
Visit 11	Day 143	>= Day 129 to <= Day 173
Visit 12	Day 203	>= Day 174 to <= Day 233
Visit 13	Day 263	>= Day 234 to <= Day 314
Visit 14	Day 365	>= Day 315 to <= Day 410
3 Months after 1 Year Treatment	Day 456	>= Day 411 to <= Day 501
6 Months after 1 Year Treatment	Day 547	>= Day 502 to <= Day 592
9 Months after 1 Year Treatment	Day 638	>= Day 593 to <= Day 684
12 Months after 1 Year Treatment	Day 730	>= Day 685 to <= Day 775
15 Months after 1 Year Treatment	Day 821	>= Day 776 to <= Day 866
18 Months after 1 Year Treatment	Day 912	>= Day 867 to <= Day 957
21 Months after 1 Year Treatment	Day 1003	>= Day 958 to <= Day 1049
24 Months after 1 Year Treatment	Day 1095	>= Day 1050 to <= Day 1112
Visit 15 (14-day follow-up)	Day of the last dose of study	>= day of the last dose of study drug+14

	drug+14 days	
Termination Visit [3]	Termination Visit during treatment period	

[1] Relative to the date of the first dose of study drug. For example, Day 1 = the date of the first dose of study drug.

[2] The study days evaluated for windows of visits during treatment period are on or prior to the last dose day.

[3] For subjects who decide not to continue in the study at any time (i.e., eCRF check box for “Continuing” is answered ‘No’), the Termination Visit is performed (as per Protocol Section 9.1.14). This is available for entry at any time as a separate visit on eCRF. The study day for the termination visit will be assigned relative to the first dose of study drug.

Visit windows for ECG measurements:

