Derived Visit	Target Study Day [1]	Window [2]
Baseline	Day 1	Days <= 1
Visit 14	Day 365	>= Day 2 to <= Day 547
12 Months after 1 Year Treatment	Day 730	>= Day 548 to <= Day 914
24 Months after 1 Year Treatment	Day 1095	>= Day 915 to <= Day 1112
Visit 15 (14-day follow-up)	Day of the last dose of study drug+14 days	>= day of the last dose of study drug+14
Termination Visit [3]	Termination Visit during treatment period	

[1] Relative to the date of the first dose of study drug. For example, Day 1 = the date of the first dose of study drug.

[2] The study days evaluated for windows of visits during treatment period are on or prior to the last dose day.

[3] For subjects who decide not to continue in the study at any time (i.e., eCRF check box for “Continuing” is answered ‘No’), the Termination Visit

is performed (as per Protocol Section 9.1.14). This is available for entry at any time as a separate visit on eCRF. The study day for the termination visit will be assigned relative to the first dose of study drug.

Visit windows for Physical Exam measurements:

Derived Visit	Target Study Day [1]	Window [2]
Baseline	Day 1	Days <= 1
Visit 3	Day 15	>= Day 2 to <= Day 22
Visit 4	Day 29	>= Day 23 to <= Day 36
Visit 5	Day 43	>= Day 37 to <= Day 50
Visit 6	Day 57	>= Day 51 to <= Day 64
Visit 7	Day 71	>= Day 65 to <= Day 78
Visit 8	Day 85	>= Day 79 to <= Day 92
Visit 9	Day 99	>= Day 93 to <= Day 106
Visit 10	Day 113	>= Day 107 to <= Day 239
Visit 14	Day 365	>= Day 240 to <= Day 547
12 Months after 1 Year Treatment	Day 730	>= Day 548 to <= Day 914
24 Months after 1 Year Treatment	Day 1095	>= Day 915 to <= Day 1112
Visit 15 (14-day follow-up)	Day of the last dose of study drug+14 days	>= day of the last dose of study drug+14
Termination Visit [3]	Termination Visit during treatment period	

[1] Relative to the date of the first dose of study drug. For example, Day 1 = the date of the first dose of study drug.

[2] The study days evaluated for windows of visits during treatment period are on or prior to the last dose day.

[3] For subjects who decide not to continue in the study at any time (i.e., eCRF check box for “Continuing” is answered ‘No’), the Termination Visit is performed (as per Protocol Section 9.1.14). This is available for entry at any time as a separate visit on eCRF. The study day for the termination visit will be assigned relative to the first dose of study drug.

Visit Day is calculated by (Visit date – date of the first dose of study drug + 1).

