The following conventions will be used for the derived visits with respect to safety variables:

1. If more than one actual visit date (including the unscheduled visits) falls within the same window, the visit closest to the target study day will be considered for analysis.
2. If 2 actual visit dates within a window are at the same distance from the target study day, the later visit with non-missing data will be considered for analysis. If repeated measurements are all taken on the same day, then the last measurement will be used.
3. Values recorded at Termination Visit will be mapped to the derived visit based on the window where the actual visit date falls in per rules 1 and 2 above.
4. Given the rules for completing the Termination Visit on eCRF (as defined in Protocol Section 9.1.14), the results recorded at Termination Visit will be summarized in the safety tables at both derived visit based on rule 3 above and at Termination Visit.

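### The ECG window for Visit 14 (target Day 365) opens at Day 2, so some short-exposure ECGs are tabulated as one-year results.

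*SAP*

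**What the plan says.** SAP 10.3 has three window tables. The ECG table has one derived treatment visit before the second-year row: Visit 14, target Day 365, window ">= Day 2 to <= Day 547". The next row, target Day 730, is ">= Day 548 to <= Day 914". For the same Visit 14, the laboratory, vital-sign and C-SSRS table uses ">= Day 315 to <= Day 410" and the physical exam table uses ">= Day 240 to <= Day 547".

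The windows cover the range "during which an actual visit (scheduled or unscheduled) may occur". Four rules in SAP 10.3 then decide what enters a row:

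- Rule 1: if several visits fall in one window, the one nearest the target day is used.
- Rule 3: "Values recorded at Termination Visit will be mapped to the derived visit based on the window where the actual visit date falls in".
- Rule 4: termination values also appear in a separate Termination Visit row.
- Footnote [2]: treatment-period windows only take days up to and including the last dose day.

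SAP Appendix 1 schedules ECGs at screening, at Visit 14 or termination, and yearly after that, with extra ECGs when clinically indicated. Protocol 9.1.14 requires one 12-lead ECG at early termination. SAP 13.3 tabulates QTcF thresholds, QTcF changes and the interpretation shift by post-baseline timepoint. It lists no any-post-baseline count. SAP 13.4 does list one for vital signs, covering scheduled and unscheduled values.

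**The concern.** Change from baseline in the 12-lead ECG is a stated safety endpoint (Protocol 6.2.2). A reader of the Visit 14 / Day 365 row will take it as the finding after about a year of treatment. For a subject who leaves early, the termination ECG is usually the only post-baseline ECG, so rule 1 has nothing nearer Day 365 to prefer and the early ECG takes that label. One row then holds ECGs after a year on drug and ECGs after a few weeks. Visit 14 also means a different span of exposure in the ECG tables than in the laboratory and vital-sign tables.

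There is a second effect. An early unscheduled ECG in a subject who later has a Visit 14 ECG is dropped by rule 1. Without an any-post-baseline row, a QTcF outlier on that ECG is left only in the listings.

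**Working it through.** **Inputs.** Target days and window edges come from SAP 10.3, the 12-week titration and the taper table from SAP 6, and the ECG schedule from SAP Appendix 1 and Protocol 9.1.14.

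**1. Reproducing the window edges.** Most edges are midpoints between adjacent targets.

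- ECG upper edge: (365 + 730)/2 = 547.5, so Day 547. Reproduced.
- Laboratory Visit 14: (263 + 365)/2 = 314, so it opens at Day 315; (365 + 456)/2 = 410.5, so it closes at Day 410. Reproduced.
- Physical exam Visit 14: (113 + 365)/2 = 239, so it opens at Day 240. Reproduced.
- ECG lower edge: (1 + 365)/2 = 183, so a midpoint rule would open it at Day 184. The SAP has Day 2. Not reproduced.

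Day 2 does follow from another convention: in all three tables the first post-baseline window opens the day after Day 1. In the laboratory and physical exam tables that first visit is Visit 3, target Day 15, window ">= Day 2 to <= Day 22", so the stretch is small. For ECG the first target is Day 365.

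**2. Width.**

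- ECG Visit 14: 547 − 2 + 1 = 546 days, with 365 − 2 = 363 before the target and 547 − 365 = 182 after it.
- Laboratory Visit 14: 410 − 315 + 1 = 96 days.
- Titration days in the ECG window (Days 2–84): 83, and 83/546 = 15.2%.
- Days before Day 184: 182, and 182/546 = 33.3%.
- Days outside the laboratory Visit 14 window: 546 − 96 = 450, and 450/546 = 82.4%.

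These are shares of calendar days, not of ECGs.

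**3. Applying rules 1 and 3 with footnote [2].**

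| ECGs after Day 1 | Last dose | Reported as Visit 14 by the SAP | With a lower edge of Day 184 or 315 |
|---|---|---|---|
| Unscheduled Day 10, Visit 14 Day 365 | after Day 365 | Day 365 | Day 365 |
| Unscheduled Day 10, Visit 14 ECG missed | after Day 547 | Day 10 | none |
| Termination Day 20, still dosing | Day 27 | Day 20 | none |
| Termination Day 22 | Day 20 | none (footnote [2]) | none |
| Unscheduled Day 10, termination Day 60, then taper | Day 67 | Day 60 | none |

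**4. Does footnote [2] prevent the mapping?** Not for subjects who taper. Protocol 9.1.14 dispenses taper drug at the termination visit, and SAP Table 5 gives at least one taper week from 150 mg/day upward. Their termination ECG therefore precedes the last dose. By SAP Tables 1 and 2, 150 mg/day starts in Week 9, that is, Day 8 × 7 + 1 = 57. Table 5 shows no taper for 50 or 100 mg/day and has no row for 12.5 or 25 mg/day. Earlier terminations are mapped only if the subject is still dosing on the visit day.

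**5. Effect on the reported mean, by assumption only.** Let f be the share of early ECGs in the row and e their mean change as a fraction of the one-year change. Reported/true = (1 − f) + f × e. The documents give neither f nor e.

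| f | e = 0 | e = 0.5 | e = 1 |
|---|---|---|---|
| 5% | 0.95 | 0.975 | 1 |
| 10% | 0.90 | 0.95 | 1 |
| 20% | 0.80 | 0.90 | 1 |
| 30% | 0.70 | 0.85 | 1 |

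If early ECGs show larger changes, the ratio exceeds 1: f = 20% and e = 1.5 give 0.80 + 0.30 = 1.10.

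**The case against.** The best defence is that the protocol already pairs the two visits. The flow chart column is Visit 14 or termination, with one set of procedures, and only one ECG is planned in the first year, so a wide window keeps every ECG in a table. The SAP says openly that its analysis windows differ from the protocol's. The study is descriptive (SAP 10.1), and all ECGs are listed by subject. This explains the design but not the label: rule 4 already gives termination ECGs their own row, so the Day 365 row does not need them.

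Four stronger readings are tempting, and the documents do not support them.

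- **That Visit 14 is the only first-year QTcF result.** It is the only derived-visit row before the second-year window. The Termination Visit row is separate.
- **That the row is biased towards no effect.** This needs f above 0 and e below 1. ECGs done because clinically indicated could be enriched for abnormalities and raise outlier percentages. Many early ECGs need not be low-dose either: of the 313 days from Day 2 to Day 314, 230 (Days 85–314, 73%) follow the scheduled titration.
- **That every early ECG enters the row.** Rule 1 drops an unscheduled ECG when one nearer Day 365 exists, and footnote [2] excludes ECGs after the last dose.
- **That the physical exam windows need the same repair.** Their Visit 10 window, ">= Day 107 to <= Day 239", ends at the midpoint of Days 113 and 365. Ending it at Day 128 and opening Visit 14 at Day 315 would leave Days 129–314 in no window.

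**Conclusion.** The point holds as a matter of labelling and mapping. Under the stated rules, an on-drug termination ECG from as early as titration, or an unscheduled ECG with no nearer alternative, is reported as Visit 14 / Day 365. The window is 546 days against 96 for laboratory tests, and its lower edge is the one Visit 14 edge in SAP 10.3 that is not a midpoint. This conclusion needs no assumption about drug effect. It does rest on reading footnote [2] as limiting rule 3, which the SAP does not say outright; if it does not, more termination ECGs are mapped. The size and direction of any bias cannot be derived from the documents. The change is worth making before tables are produced, but it does not put the study's conclusions in doubt.

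**What to change.** In SAP 10.3 and 13.3:

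1. Raise the lower edge of the ECG Visit 14 window. Day 184 follows the midpoint convention and leaves 547 − 184 + 1 = 364 days, nearly symmetric about Day 365. Day 315 matches the laboratory table's lower edge and leaves 547 − 315 + 1 = 233 days.
2. Add an early on-treatment ECG interval from Day 2 to the day before that edge (Day 183 or Day 314). No ECG is scheduled there, so rule 1 needs a stated target day or selection rule for it.
3. Add an any-post-baseline QTcF outlier row covering scheduled and unscheduled ECGs, as SAP 13.4 does for vital signs. Narrowing the window without this would leave some early outliers only in listings.
4. State whether footnote [2] limits rule 3, so that a termination ECG after the last dose has one defined place.

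Leave the later ECG windows and the physical exam windows as they are. The cost is SAP wording, a smaller n in the Visit 14 row and slightly more programming. No data collection changes, and termination ECGs stay in their own row.

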13.4 Analysis of Vital Signs

All vital signs will be listed by-subject. Baseline measurement is defined as the last available measurement prior to the first dose. Post-baseline timepoints will be derived as per rules included in [Section 10.3](#). For the safety population the following summary tables will be generated for vital signs by safety evaluable subgroups and overall for the safety population:

- Summary statistics (n, mean, standard deviation, median, minimum, and maximum) of the baseline value, the observed value at each post-baseline timepoint and the corresponding change from baseline.
- Number and percentage of subjects with at least one post-baseline (scheduled or unscheduled) vital sign measurement meeting any of these criteria:

- Systolic Blood Pressure: <90 mmHg, >140 mmHg, >160 mmHg
- Diastolic Blood Pressure: <50 mmHg, >90 mmHg, >100 mmHg
- Pulse Rate: <60 bpm, >100 bpm
- Body Weight: decrease of $\geq 7\%$ from baseline and increase of $\geq 7\%$ from baseline
- Respiratory rate: <12 breaths/min, > 20 breaths/min
- Temperature: >38.0 °C, <36.0 °C

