13.6 Columbia Suicide Symptoms and Signs Rating Scale (CSSRS)

C-SSRS Ideation, Intensity and Behavior are collected at baseline and all post-baseline visits. Summary results of response to each question (number and percentage of subjects) will be reported by safety evaluable subgroups and overall and by study visit. The summary table will include all subjects in the safety population.

At each visit, C-SSRS responses will be mapped into Columbia-Classification Algorithm of Suicide Assessment events on as follows:

- Complete suicide = as captured in the safety database (adverse events and/or reason for discontinuation)
- Suicide attempt: “Yes” on “Actual attempt” question
- Preparatory acts towards imminent suicidal behavior: “Yes” on any of the following
 - “Aborted attempt”, or
 - “Interrupted attempt”, or
 - “Preparatory acts or behavior”.
- Suicidal ideation: “Yes” on any of the following:
 - “Wish to be dead”, or
 - “Non-specific active suicidal thoughts”, or
 - “Active suicidal ideation with any methods (not plan) without intent to act”, or
 - “Active suicidal ideation with some intent to act without specific plan”, or
 - “Active suicidal ideation with specific plan or intent”.

New onset suicidality and worsening suicidality during double-blind-phase will be assessed via a shift analysis from baseline to each post-baseline visit and to any post-baseline visit. The following shift categories will be defined:

Suicidality	Baseline Event	Any post -baseline and by visit event
New onset	No suicidal ideation and no behavior (i.e., no suicide attempt or no preparatory acts towards	Any ideation (i.e., suicide ideation) or any behavior (i.e., complete suicide, suicide attempt, or

	imminent suicidal behavior)	preparatory acts towards imminent suicidal behavior)
Worsening	Suicidal ideation	Complete suicide, or suicide attempt, or preparatory acts towards imminent suicidal behavior
	Preparatory acts towards imminent suicidal behavior	Complete suicide or suicide attempt
	Suicide Attempt	Complete suicide

The number and percentages of subjects in each of the shift categories defined above will be reported by safety evaluable subgroups and overall for all subjects included in the safety population. Missing C-SSRS responses will not be imputed.

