15 GENERAL PROGRAMMING SPECIFICATIONS

15.1 Format

Computer generated tables described in this analysis plan will adhere to the following specifications.

- (a) Summary tables displaying results by derived visit as defined in [Section 10.3](#).
- (b) By-subject listing will display results in chronological order of visit dates and will include both scheduled and unscheduled visits.
- (c) The estimated mean and median for a set of values will be reported to one more decimal place than the raw (observed) data and rounded appropriately. The standard errors (or standard deviations [SD]) will be reported to two additional decimal places than the raw (observed) data and rounded appropriately. For example, for age (with raw data in whole years):

N	XX
Mean (SD)	XX.X (X.XX)
LS Mean (SE)	XX.X (X.XX)
Median	XX.X
Range	XX-XX

- (d) Data in columns of a table will be formatted as follows:
 - i. Alphanumeric values will be left-justified (in mixed and upper- and lower-case)
 - ii. Whole numbers (e.g., counts) will be right justified
 - iii. Numbers containing fractional portions will be decimal aligned
- (e) All fractional numeric values will be reported with a zero to the left of the decimal point (e.g., 0.12-0.3).
- (f) Percents will be reported to one decimal place.
- (g) Dates will be reported in SAS DATE9. format (eg, 29MAR2007). Missing portions of dates should be represented on subject listings as dashes (--MAR2007). Dates that are missing because they are not

applicable for the subject should be listed as “N/A”, unless otherwise specified.

- (h) The table should be typed in Arial 10-point font. The table title should be typed in Bold Initial Caps, Arial 10-point font, beginning with the word Table X, Title.
- (i) Header (or footer) information for all tables, figures, and listings (TFLs) will include the protocol number, table status (draft or final) and the date and time the table was created.
- (j) Any TFLs generated prior to database lock or completion of TFL validation will be marked “Draft”.

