- a. After 12 months of participation in the open-label extension phase, subjects will be re-evaluated. Those who are benefiting from treatment with YKP3089 may continue use of the drug at the discretion of the investigator, until development is stopped by SK Life Science Inc, or the product is approved for marketing, or anytime at the discretion of SK Life Science Inc.
- b. Vital signs include blood pressure, heart rate (supine for 5 minutes), temperature, and respiratory rate.
- c. Height measured only at Visit 1.
- d. Brief neurological exam should be done only if symptoms require
- e. Administer the Baseline/Screening version of the C-SSRS at Screening. Administer the Since Last Visit version at all subsequent visits.
- f. 12-lead ECG will be performed once. Additional ECGs should be performed at any other time if clinically indicated.

- g. For female subjects of childbearing potential: If pregnancy is suspected at any time during the study, an interim test may be performed in addition to scheduled assessment.
- h. Laboratory assessment: Safety assessment includes blood chemistry and hematology. If the subject meets an exclusion criterion at Visit 1, an unscheduled laboratory sampling can be repeated for confirmation.
- i. Two blood samples will be collected for the determination of YKP3089 plasma levels: For patients that are taking YKP3089 in the morning and coming into the visits in the morning, the first blood draw will be collected upon subjects' arrival to the study unit; the second blood draw should be collected within 30 minutes to 2 hours after the medication is taken. Collect at visit 8 and/ or 9 depending on stability of dosing (doses must be stable for 2 weeks prior to these visits) of all concomitant AEDs including oxcarbazepine, topiramate, lamotrigine, lacosamide, clobazam, perampanel, levetiracetam, phenytoin and phenobarbital and YKP3089. YKP3089 PK draw is applicable for subjects on phenytoin and phenobarbital globally and all subjects at US sites.

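### The closest-to-target window rule can drop a positive Since Last Visit C-SSRS form from the by-visit tables, and SAP 13.6 does not say which forms feed the any-visit row

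*SAP*

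**What the plan says.** The first window table in SAP 10.3 covers laboratory tests, vital signs and the C-SSRS together, with 20 on-treatment windows from Visit 3 to 24 months after the first year. The rules that follow open with "The following conventions will be used for the derived visits with respect to safety variables" and make no exception for the C-SSRS. Under rule 1, in which unscheduled visits compete, if more than one visit date "falls within the same window, the visit closest to the target study day will be considered for analysis". Rule 2 settles ties in favour of the later visit. Rules 3 and 4 map a Termination Visit to its derived visit and also give it a row of its own. Table footnote 2 limits on-treatment windows to days up to the last dose.

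On the instrument, SAP Appendix 1, footnote e, gives the baseline version at screening and then: "Administer the Since Last Visit version at all subsequent visits".

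SAP 13.6 summarises each question by visit, maps the answers to ideation, preparatory acts, attempt or completed suicide, and says that new-onset and worsening suicidality "during double-blind-phase will be assessed via a shift analysis from baseline to each post-baseline visit and to any post-baseline visit". Completed suicide is taken from the safety database.

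Two neighbouring sections name the source of their any-time counts. SAP 13.2 uses scheduled and unscheduled results for the overall laboratory shift, and SAP 13.4 counts subjects with "at least one post-baseline (scheduled or unscheduled) vital sign measurement meeting any of these criteria". SAP 13.6 has no such sentence. SAP 15.1(a) sets the general format: "Summary tables displaying results by derived visit as defined in" Section 10.3.

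**The concern.** A laboratory value describes the subject on the day it is taken, so keeping the value nearest the target day is a reasonable way to obtain one value per visit. A Since Last Visit C-SSRS is different. It records what happened since the previous form, and the next form starts where it ends. If two forms fall in one window and one is set aside, its interval is missing from the by-visit table. Ideation that persists may be reported again on the next form. An attempt, or ideation confined to the dropped interval, would not be.

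The C-SSRS is a named safety endpoint in Protocol 6.2.2 and SAP 7.2, and long-term safety is a study objective. Compared with a count over all forms, a count over selected forms can be equal or lower but never higher. Any error therefore understates suicidality.

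**Working it through.** The plan states no figure on this point, so there is nothing to reproduce. The check takes the SAP 10.3 windows, the Protocol Section 9 visit windows (±2 days for Visits 3 to 10, ±7 days for the others) and rules 1 and 2.

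**1. Can on-schedule visits collide?** Compare each target's distance to the nearer edge of its analysis window with the protocol allowance.

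- Visits 3 to 10: the smallest distance is 6 days (for example Visit 4: 29 − 23 = 6), against an allowance of 2.
- Visits 11 to 14: the smallest is 14 days (Visit 11: 143 − 129 = 14), against 7.
- Extension visits: Protocol 9.1.16 counts every 3 months from Visit 14. Visit 14 may be 7 days off target and each later visit a further 7, so 14 in all. The smallest distance is 17 days (24-month visit: 1112 − 1095 = 17).

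All on-schedule visits therefore fall in separate windows. A form is dropped only when an unscheduled, off-schedule or termination visit shares a window with another visit.

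**2. Is there room for a second visit?** Widths are 14 to 22 days for Visits 3 to 10 (Visit 4: 36 − 23 + 1 = 14; Visit 10: 128 − 107 + 1 = 22) and 45 to 96 days from Visit 11 on (Visit 11: 173 − 129 + 1 = 45; Visit 14: 410 − 315 + 1 = 96). Protocol 9.2 allows unscheduled visits at any time.

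**3. Worked case, subject on treatment throughout.** Visit 11 is held on Day 143 and is negative. An unscheduled form on Day 165 reports ideation. Visit 12 is held on Day 203.

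- Days 143 and 165 both lie in the Visit 11 window (Days 129 to 173).
- Distances from target: |143 − 143| = 0 and |165 − 143| = 22, so Day 143 is selected.
- The Day 203 form covers only the time since Day 165.

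If the ideation did not continue past Day 165, no selected form carries it.

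**4. Conditional case with a termination visit.** Visit 6 on Day 55 (inside ±2) reports ideation and a termination visit follows on Day 58. Distances from target Day 57 are 2 and 1, so Day 58 is selected and Day 55 is dropped. The termination row shows the Day 58 form, not the Day 55 form. Under footnote 2 this holds only if dosing continued through Day 58. Otherwise the termination form does not enter the Visit 6 window and Day 55 is kept.

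**5. How often is a form dropped once an extra one exists?** A simulation placed one extra form on a uniformly random day from 2 to 410, with the scheduled visit uniform within its protocol window (both assumptions). The extra form was dropped in about 86% of runs and the scheduled form in about 11%; both fell on the same day in about 3%. This says nothing about how often extra forms occur.

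**6. Size if the any-visit row also uses selected forms only.** Missed subjects per 1,000 = 1,000 × p × f, where p is the true any-time rate and f the share of those subjects positive only on a form not selected. Neither value is in the documents. Assuming p of 1% to 5% and f of 5% to 20%, the range runs from 1,000 × 0.01 × 0.05 = 0.5 to 1,000 × 0.05 × 0.20 = 10.

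**The case against.** The case for leaving the plan alone has real content.

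- SAP 13.6 does not cite 10.3, as 13.2 to 13.5 do. But 10.3 names the C-SSRS in its window table and gives it its own baseline and Visit 2 rows, so the rule does apply to the by-visit tables.
- A reader might infer that a positive form also disappears from the any-visit row. The documents do not say so. The wording of 13.6 fits all completed forms equally well, 15.1(a) concerns results shown by derived visit, which an any-time row is not, and the table templates are in separate documents. What stands is that the source is unstated, and the general format may lead a programmer to selected forms only.
- A reader might expect extension visits to drift into one window, or the visit at which a subject withdraws to be lost. Step 1 rules out the first for visits held on schedule. Rule 4 gives the termination form its own row, so only another form can be displaced.
- A reader might suppose that the displaced forms are the likeliest to be positive. Nothing supports this. Protocol 9.2 does not require a C-SSRS at unscheduled visits, so how many such forms exist is unknown.
- Other outputs remain. Completed suicide is unaffected, suicidality recorded as an adverse event is counted in tables that do not use visit windows, and listings show every visit. None of these puts ideation, preparatory acts or attempts back into the C-SSRS tables.
- The study is descriptive, so no test is affected, and the double-blind reference looks like a wording slip rather than evidence of lost data.

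**Conclusion.** The point holds for the by-visit C-SSRS tables: a stated rule can discard the only form covering an interval, and the effect can only lower counts relative to all forms. It is confined to windows shared with an unscheduled, off-schedule or on-treatment termination visit, and to events not reported again on a selected form. For the any-visit row it is an ambiguity, not a demonstrated loss. The double-blind period does not exist in this study and needs correcting in any case.

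The number affected cannot be derived from the documents. The range of 0.5 to 10 per 1,000 rests wholly on assumed rates and on the selected-forms reading of the any-visit row. This should be fixed because the endpoint matters and the remedy is cheap, but the documents do not support calling it essential.

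**What to change.** In SAP 10.3, exempt the C-SSRS category and shift tables from rules 1 and 2. For each window, use the most severe mapped category over all forms in it, in the order completed suicide, attempt, preparatory acts, ideation, none. For the question-level table, count a Yes if any form in the window has a Yes. Keep the separate Termination Visit row.

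In SAP 13.6, state that the any post-baseline row uses all scheduled, unscheduled, termination and Visit 15 forms completed after first dose. Report a pre-dose Visit 2 form separately: the C-SSRS baseline is Visit 1, and Protocol 9.1.2 allows the first dose after the Visit 2 procedures or the next morning. Replace the double-blind reference with the open-label treatment period through Visit 15.

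No new data are needed, and SAP Section 4 allows revision before database lock. The cost is a few sentences and a small programming change. Event counts may rise slightly.
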